However, due to the only recent identification of this process, there has not yet been an attempt to stimulate the pharyngeal muscles with noradrenergic drugs in sleeping humans. Now, more than ever, the stage has been set for stimulating the pharyngeal muscles across both NREM and REM sleep.

II. SPECIFIC AIMS

To determine the effect of noradrenergic and antimuscarinic on genioglossus activity and OSA severity. We hypothesize that existing drugs with these neurotransmitter profiles could (partially) restore pharyngeal muscle activity in humans during sleep.

Specifically, we will test this hypothesis by assessing;

1. The effect of pseudoephedrine (an α 1-adrenergic agonist) combined with diphenhydramine (an antihistaminic with sedative properties and with antimuscarinic action) on EMG_{GG} during sleep (PART D).

III. SUBJECT SELECTION

We will recruit a group of subjects with OSA. These subjects will be recruited from the community and be between 21-65 years old. The purpose of studying patients with OSA is to determine what effect this drugs will have on improving the patient's OSA severity.

a) Obstructive Sleep Apnea Patients (n= 15): Patients with OSA will be recruited from our clinical sleep laboratory at Brigham and Women's Hospital, as well as from our existing database of OSA patients. These individuals will be otherwise healthy (except for well-controlled hypertension; defined as systolic blood pressure <140 mmHg and diastolic <90 mmHg) with no active medical problems and on no medication that could affect respiration or muscle control. All will be 21-65 years of age. Both men and women will have an apnea-hypopnea index (AHI) >15 events/hr during supine NREM sleep. These individuals will be recruited to encompass a large range of AHI's (from 10 to >60/hour).

b) Exclusion criteria:

- Any active medical condition other than well controlled hypertension, hyperlipidemia, gastroesophageal reflux disease, depression.
- Any medication known to influence breathing, sleep/arousal or muscle physiology.
- Claustrophobia.
- Inability to sleep supine.
- Allergy to lidocaine, Oxymetazoline HCl, pseudoephedrine HCl, diphenhydramine.
- Individuals with underlying cardiac disease, such as arrhythmias.
- History of seizures
- History of moderate or severe renal impairment
- For women: Pregnancy.

We will consider all applicants regardless of sex, race, color, creed, or national origin.

DETAILED PROTOCOL

Version: October 17, 2016

IV. SUBJECT ENROLLMENT

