Two overnight sleep studies will be performed approximately 1 week apart: a placebo night and a pseudoephedrine-plus-diphenhydramine (120+50mg PO, DAW1033D) night, in double-blinded randomized control design. For each night, the subjects will arrive at the sleep laboratory at approximately 7:00pm. A physician will complete a complete physical and medical history. The placebo or DAW1033D will be administered 30 minutes before lights out. At least 15 minutes of quiet wakefulness will be recorded to quantify the subject's awake EMG_{GG} activity. Subjects will then be allowed to fall asleep during which we will assess EMG_{GG} activity throughout the rest of the evening (see below for details).

Measurements and equipment:

Subjects will be instrumented with standard polysomnography (PSG) recording sensors. Sleep stage and arousals will be measured with electrodes pasted on to the scalp, face, chin and chest (EEG, EOG, EKG,

DETAILED PROTOCOL

Version: October 17, 2016

chin EMG). Paste-on EMG electrodes will be placed over the anterior tibialis muscle to detect leg movements. Respiratory effort belts will be placed around the chest and abdomen to measure breathing movements. Oxygen saturation will be measured continuously with a pulse oximetry probe placed on either the fingertip or earlobe. Snoring will be detected with a small microphone positioned over the suprasternal notch. Body position will be recorded with a sensor taped to the thoracic belt. Each of these devices is standard for diagnostic PSG and should not be uncomfortable.

One nostril and the back of the throat will be anesthetized with 4% lidocaine; only 2–3 ml (80–120 mg) of lidocaine is used. One small, flexible pressure-tipped catheter (Millar) will then be inserted through the anesthetized nostril until the tip of the catheter is located just above the epiglottis (or in the esophagus) by visual inspection through the mouth; the catheter is then taped to the nose to prevent movement. This catheter is used to assess upper airway negative pressure and to calculate airflow resistance both awake and during sleep.

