After these test during wakefulness, the subjects will be given Desipramine (200 mg PO) /placebo to take and then be connected to a positive/negative pressure source (Philips-Respirronics, Murrysville, PA) to enable rapid switching between pressure levels and allowed to fall asleep on 4 cmH₂O of CPAP. When stable sleep is reached, the CPAP will be modified to the level that abolishes flow limitation, as determined by the airflow waveform. Five minutes of stable sleep will then be recorded. Following this baseline recording period, the CPAP level will be reduced to varying suboptimal pressures for several minute

DETAILED PROTOCOL

Version: October 17, 2016

intervals to see how the genioglossus responds to airway collapse. In the case of controls, the suboptimal level required to collapse the airway may require negative pressures. If the subject awakens during the suboptimal pressure drop, the pressure will be immediately returned to the holding pressure until stable NREM sleep is again achieved. We have performed this technique in numerous healthy controls and OSA patients with no complications to date. Furthermore, it is our experience that the response to negative pressure drops which is often used in healthy controls is similar to the suboptimal positive pressures used in OSA patients.

After approximately 4 hours of sleep, we will remove the CPAP and ask the subjects to sleep in the lateral position for the duration of the evening to minimize pharyngeal resistance similar to previous studies of this kind (25). As much data will be recorded from NREM and REM sleep as possible over the night. Following completion of the study, all equipment will be removed, and the subject will be able to sleep in the laboratory free from equipment for the rest of the night. Alternatively, if the subject feels alert enough to leave, they may do so.

Data Analysis:

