Muscle activity will be quantified using standard procedures described in our previous studies (1, 23, 24). Briefly, the raw EMG_{GG} signal will be rectified and smoothed with a 100 msec window. The peak phasic, as well as tonic, activity of the smoothed signal will be identified for each breath. Data from quiet wakefulness (free of swallowing and movement artifacts) will be averaged to determine the peak phasic and tonic activities during this state. The same will be done for stable NREM and REM sleep (free of arousals and other artifacts). Both NREM and REM sleep will be analyzed, recognizing that REM is less frequent on these drugs. Pharyngeal muscle responsiveness will be determined by calculating the slope and intercept of the epiglottic pressure versus muscle EMG relationship.

Reimbursement

Subjects will receive \$100/night for participation in each overnight study (TOTAL = \$200 for each PART of the study). Reimbursement for parking expenses will be provided.

If the subjects will repeat a part or the entire protocol because of insufficient data collection, they will be reimbursed \$100 for any extra night.

VI. BIOSTATISTICAL ANALYSIS

Subjects will be prospectively enrolled until 10 had completed both study nights. Sample size was chosen to facilitate detection of a clinically-important $50 \pm 50\%$ reduction in AHI. Calculations were based on previous studies conducted in our laboratory. To account for a ~30% failure rate approximately 13 patients will be enrolled in the study.

In order to reduce the influence of potential outlier, data will be expressed as median [interquartile range] and data on placebo vs DAW1033D will be compared using Wilcoxon test. A p value < 0.05 will be considered as statistically significant.

In the pilot study using the noradrenergic drug desipramine, the average difference in EMG_{GG} activity (between the placebo night and the drug night, with EMG_{GG} quantified as a percentage of wakefulness) was $47 \pm 20\%$. In order to detect this difference with 80% power and a 5% level of significance, 6 subjects would need to be studied.

DETAILED PROTOCOL

Version: October 17, 2016

VII. RISKS AND DISCOMFORTS

We believe that the risks associated with participation in this study are minimal. All study procedures have been conducted in our laboratory without serious incident. Anticipated risks and discomforts are listed below:

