1. The equipment used for assessing sleep (paste on electrodes) is standard and poses no risk. The electrodes may be mildly uncomfortable and could cause some sleep interruption. Thus subjects may feel somewhat tired the day following this study.
2. Pharyngeal Pressure Catheter: Inserting the pressure catheter through the nostril and into the pharynx may be uncomfortable and could cause gagging or even vomiting. The anesthetized and fasting state substantially reduces the risk of discomfort or complications. As the subject will have a catheter in his/her pharynx and a nasal mask in place, the risk of aspiration must be considered. However, this has never been encountered after hundreds of similar studies. The catheter, once in place, does not gag the subject and the mask can easily be removed. Overall, the risk of aspiration is minimal.
 - i. Lidocaine. If the subjects have any history of lidocaine allergy, they will be excluded from the study. Excessive use of lidocaine can cause seizures, but this is reported with much higher doses than will be utilized in this study. However, subjects will be informed that lidocaine has an unpleasant taste.
3. Intramuscular EMG Determination: Needle insertion may be painful although the mucosa is topically anesthetized with lidocaine. We have found this pain to be similar to venipuncture and well tolerated. Discomfort is minimal once the needle is removed and the wire is left in place. A small amount of bleeding and/or a small bruise may occur. Both the needles and wires are sterilized. However, intramuscular or surface infection could occur, as it is impossible to sterilize the inside of the mouth. We have never encountered this problem or heard of it occurring elsewhere. There may be some residual soreness in the tongue for several hours after the wires are removed.
4. Pseudoephedrine: this drug is available at the dose of 15, 30, 60 and 120 mg as over-the-counter medication of nasal congestion and cold relief. Common side effects include arrhythmia, tachycardia, palpitations, nervousness, excitability, restlessness, dizziness, weakness, insomnia, headache, drowsiness. Other side effects may include anorexia, constipation, diarrhea, hypertension, dry throat, ischemic colitis, nausea, vomiting, xerostomia, dysuria, polyuria, urinary retention, tremor, weakness, blurred vision, diplopia, dry nose, dyspnea, nasal congestion, thickening of bronchial secretions, wheezing, tinnitus.

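### The dosing step in Section V names the wrong active drug: desipramine 200 mg instead of pseudoephedrine 120 mg plus diphenhydramine 50 mg (DAW1033D)

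*Combined protocol and SAP*

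**What the plan says.** Section V contains two instructions on what the subject takes, and they name different drugs.

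- The paragraph headed Protocol defines the two nights as "a placebo night and a pseudoephedrine-plus-diphenhydramine (120+50mg PO, DAW1033D) night", double-blind and randomised, and then gives a dosing rule: "The placebo or DAW1033D will be administered 30 minutes before lights out".
- Later in the section, after the wakefulness manoeuvres and before connection to the pressure source, the text says "After these test during wakefulness, the subjects will be given Desipramine (200 mg PO) /placebo to take".

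Outside Section V, the single specific aim in Section II concerns pseudoephedrine combined with diphenhydramine. The allergy exclusion in Section III reads "Allergy to lidocaine, Oxymetazoline HCl, pseudoephedrine HCl, diphenhydramine". Section VI states that "data on placebo vs DAW1033D will be compared using Wilcoxon test". Section VII has drug entries for lidocaine, pseudoephedrine, diphenhydramine and the pseudoephedrine-diphenhydramine combination. Desipramine is named once more, in the last paragraph of Section VI, which begins "In the pilot study using the noradrenergic drug desipramine".

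**The concern.** The later sentence sits in the running order of the study night, where staff would look to see what is given and when. It states a drug, a dose and a route, and it offers placebo as the blinded alternative, so it reads as the trial's treatment instruction. It is current text under the October 17, 2016 version header and is fully legible; it is neither a record of superseded wording nor an effect of redaction.

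Two things are at stake if it were acted on:

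- **Safety.** Subjects would receive a drug and dose for which this protocol gives no risk description and no drug-specific exclusion.
- **Inference.** Nights analysed as DAW1033D would be desipramine nights, so the planned paired comparison would estimate the effect of a different drug. If only some staff followed the step, it would estimate a mixture of two drugs.

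**Working it through.** The plan states no figure for this point, so the check compares every place that identifies the treatment.

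| Place | Active treatment named |
|---|---|
| Section II, only specific aim | pseudoephedrine + diphenhydramine |
| Section III, allergy exclusion | pseudoephedrine and diphenhydramine listed; desipramine absent |
| Section V, Protocol, two-night design | DAW1033D, 120 + 50 mg PO |
| Section V, Protocol, dosing rule | DAW1033D |
| Section V, step after the wakefulness tests | **desipramine 200 mg PO** |
| Section VI, planned comparison | DAW1033D |
| Section VI, EMG sample-size paragraph | desipramine, as a past pilot only |
| Section VII, drug risks | pseudoephedrine, diphenhydramine and their combination; desipramine absent |

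**Counts.** Desipramine is named 2 times: the dosing step and the pilot. The code DAW1033D is named 3 times: twice in the Protocol paragraph of Section V and once in Section VI. Desipramine is 0 of the 4 agents in the allergy exclusion and 0 of the 4 drug entries in Section VII.

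**Could the sentence be right on another reading?**

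1. *A third arm.* No. The design has two nights and names the content of both.
2. *A co-treatment given with DAW1033D.* No. The sentence pairs desipramine with placebo as alternatives, and no other section mentions giving both.
3. *A different part of a larger study.* Section II labels the aim PART D, and the reimbursement text in Section V refers to parts of the study. This suggests, but does not prove, that wording was carried over from a multi-part protocol. This document describes no desipramine part, so the reading does not rescue the sentence.

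**Timing.** Giving the drug after the wakefulness tests and giving it 30 minutes before lights out can both be satisfied. The conflict concerns the drug only.

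**Does the correction affect the sample size?** No. The main calculation assumes a 50 ± 50% AHI reduction, a standardised effect of 50/50 = 1. A paired t-test at two-sided 5% and 80% power gives n = 9.94, rounded up to 10, with power 80.3% at n = 10. That reproduces the plan's 10 completers, and the drug name does not enter it. The EMG paragraph uses the desipramine pilot, with effect 47/20 = 2.35. A paired t-test has 86% power at n = 4, so the plan's 6 exceeds that requirement. That paragraph describes past data and is unaffected by which drug the dosing step names.

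**Exposure bound.** The minimum is 0 subjects if the Protocol paragraph governs. The maximum is the number enrolled if the later step governs: about 13 by Section VI, 15 by Section III.

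**The case against.** The strongest reply concerns severity. A careful reader can resolve the conflict from the document alone, because the treatment is stated clearly in the aim, design, analysis and risk sections. If blinded supplies were prepared to match the design paragraph, bedside staff would not be choosing a drug from this sentence, and no section says desipramine is supplied for this study. The general exclusions for cardiac disease and seizures would still apply.

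Much of that stands. The documents do not describe supply or dispensing, so they do not show that anyone would receive the wrong drug, and the figures of 13 and 15 are upper bounds, not estimates. For the same reason, protection by blinded supply is also an inference. General exclusions do not replace drug-specific risk text. A dosing instruction should be correct where it stands, without the reader having to compare it with five other sections.

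A second reply is that the repair may be too narrow. The same paragraph mentions controls although Section III recruits only patients with OSA, so other wording may also have been carried over. That is a reason to reread the paragraph, but it does not weaken the finding. It is also fair to note that the EMG calculation of 6 subjects rests on the desipramine pilot and so is not specific to DAW1033D. Naming the pilot drug there is accurate reporting.

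**Conclusion.** The concern holds. One operative sentence in Section V names a drug and dose that are not part of this study, and everything else that defines the treatment points to DAW1033D. It is a drafting error, not a design decision, but it must be corrected because it tells staff what a subject should swallow. Its effect on the planned comparison and on safety is conditional on the sentence being followed, which the documents neither establish nor exclude. The conclusion rests on the text alone. The idea that the wording came from a parent protocol is an inference, and the conclusion does not depend on it.

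**What to change.** In the Section V step after the wakefulness tests, replace the desipramine phrase with *DAW1033D (pseudoephedrine 120 mg plus diphenhydramine 50 mg PO) or placebo*, and add that it is given 30 minutes before lights out, as the Protocol paragraph already requires. The aim, exclusions, drug risks and planned comparison already match and need no change, and the pilot mention in Section VI can stay. While that paragraph is open, it is sensible to reread it for other carried-over wording, such as the reference to controls.

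The cost is a wording change to one sentence. It needs no additional subjects or procedures and no change to the sample size, power or test.

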5. Diphenhydramine: this drug is available at the dose of 25 and 50 mg as over-the-counter medication of allergy and cold relief. Common side effects include: sedation, sleepiness, dizziness, disturbed coordination, epigastric distress, thickening of bronchial secretions. Other side effects may include extrasystoles, hypotension, palpitations, tachycardia, blurred vision, diplopia, difficulty in micturition, urinary frequency, urinary retention, tinnitus, anorexia, constipation, diarrhea, dry mucous membranes, epigastric distress, nausea, vomiting, xerostomia.
6. Combination of pseudoephedrine and diphenhydramine: the association of these drugs is already available (at a lower dose of 60/25 mg) as over-the-counter medication for nighttime relief of allergy, sinus and cold symptoms (see for example Benadryl Allergy Sinus). The most common side effects of the combination of the drugs are constipation, diarrhea, dizziness, drowsiness, dry mouth, nose, and

DETAILED PROTOCOL

Version: October 17, 2016

throat; excitability, headache, anorexia, nausea; nervousness or anxiety, insomnia, weakness. As both drugs are commonly administered at higher doses alone, we believe that increasing the dose of the combination will not determine excessive increase in the risk of serious side effects. Furthermore, the drugs will be administered for only one night in a monitored setting: an experienced researcher will be present for the entire night checking vital signals in real time (heart rate, oxygen SaO₂, EEG), the patient will be under audio and video-surveillance. An MD will be available for the duration of the study and the following morning if necessary.

VIII. POTENTIAL BENEFITS

Although it is unlikely that there will be any direct physical benefit to the subjects from participating in this study, we will make known to each subject, if requested, some of the information we have gathered from this physiologic testing. This study provides a unique opportunity to gain insight into the specific mechanisms by which these novel drugs may improve upper airway muscle function. The results may, in the future, lead to improved strategies for the treatment of sleep apnea. However, if previously unknown abnormalities of sleep and breathing are encountered, this information will be passed onto the subject. Results can be forwarded to the primary care physician or clinician at the request of the subject.

IX. MONITORING AND QUALITY ASSURANCE

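### After the study night a subject may leave on self-judged alertness alone, and the end-of-night equipment removal does not match the whole-night signal checking described in the risk section

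*Combined protocol and SAP*

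**What the plan says.** Section V (Study Procedures), in the last paragraph before Data Analysis, says that once the study is complete "all equipment will be removed, and the subject will be able to sleep in the laboratory free from equipment for the rest of the night". It then gives the other option: "Alternatively, if the subject feels alert enough to leave, they may do so". It gives no time for either, and no other condition for leaving.

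Section VII (Risks and Discomforts), item 6, supports giving the combination above its marketed strength on two grounds. The first is pharmacological: "As both drugs are commonly administered at higher doses alone", the investigators expect no excessive rise in serious side effects. The second is the setting, a single monitored night: "an experienced researcher will be present for the entire night checking vital signals in real time", the signals being heart rate, oxygen saturation and EEG. In addition, "the patient will be under audio and video-surveillance", and a physician is available during the study and, if needed, the next morning.

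On expected effects, item 6 says: "The most common side effects of the combination of the drugs are constipation, diarrhea, dizziness, drowsiness". Item 5 says of diphenhydramine: "Common side effects include: sedation, sleepiness, dizziness, disturbed coordination, epigastric distress, thickening of bronchial secretions". Item 4 counts arrhythmia, tachycardia, palpitations, dizziness and drowsiness among the common effects of pseudoephedrine.

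For later contact, Section V places the two nights about a week apart, and Section IX plans a coordinator's call 2 to 3 weeks after the study.

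**The concern.** The only written condition for leaving is how the subject feels. Sedation can impair a person's judgement of their own alertness, and feeling alert says nothing about steadiness, heart rate or blood pressure. Section III admits subjects with well-controlled hypertension, item 4 lists hypertension as a possible pseudoephedrine effect, and blood pressure is not among the signals that item 6 says are watched. Staff following Section V as written could let a drowsy, unsteady or tachycardic subject go, and no planned contact would pick this up for about a week or more.

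There is also a mismatch between sections. Heart rate, oxygen saturation and EEG come from the sensors described in Section V and cannot be read once all equipment is off. Yet item 6 offers the checking of those signals as part of the support for the dose.

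What is at stake is subject safety on the drug night. Recording has ended by then, so the EMG and AHI data are not affected.

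**Working it through.** The plan gives no figure to reproduce here. The check compares the sections and uses simple arithmetic.

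1. **Dose against the marketed combination.** Study dose 120 mg + 50 mg (Section V, Protocol); marketed combination 60/25 mg (Section VII, item 6). Ratios: 120/60 = 2.0 and 50/25 = 2.0.

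2. **Dose against single-agent strengths.** Item 4 lists pseudoephedrine up to 120 mg. Item 5 says of diphenhydramine: "this drug is available at the dose of 25 and 50 mg as over-the-counter medication of allergy and cold relief". Ratios to the highest listed strength: 120/120 = 1.0 and 50/50 = 1.0.

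3. **Earliest equipment removal.** Dosing is 30 minutes before lights out (Section V, Protocol). CPAP comes off after about 4 hours of sleep, and a period of lateral sleep of unstated length follows. Time from dose to removal is therefore at least 0.5 h + about 4 h = about 4.5 h, plus the lateral period. This is a floor for a completed study, not an expected time. Section V aims to record as much sleep as possible over the night, so removal may come much later.

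4. **What remains after removal.**
   - Subject stays: sensor signals stop; researcher presence and audio/video surveillance may continue.
   - Subject leaves: on-site observation ends; no check at departure is stated.

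5. **Next planned contact after a drug night.**
   - Drug night first: the second night, about 1 week = about 7 days.
   - Drug night second: the coordinator's call, 2 to 3 weeks = 14 to 21 days.
   - The physician's availability the next morning is conditional on need and is not a scheduled assessment.

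6. **Exposure.** Section VI gives 10 completers and about 13 enrolled; Section III gives n = 15. At one drug night each, that is 10 to 15 drug nights; at two nights each, 2 × 10 = 20 to 2 × 15 = 30 nights, before any repeat nights.

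The length of the period without sensors cannot be computed, because no removal time is given. Nor can residual drug effect at departure, because the documents give no half-lives.

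**The case against.** The strongest reply is that this is loose wording. Equipment comes off only at study completion, so the remainder of the night may be brief. In item 6, the reference to the entire night can be read as describing the researcher's presence, with signals checked while they are being recorded. Staff are on site when a subject leaves, and heart rate has been watched in real time up to equipment removal. Each component equals a listed over-the-counter strength, is given once, and goes to subjects screened for cardiac disease. Insomnia and excitability are also listed, so the net effect on alertness is unknown.

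Much of this stands. A reader might infer that item 6 and Section V flatly contradict each other and leave a long unmonitored stretch; the documents do not show that. A reader might also infer that subjects leave with no staff check at all. That rests on silence: the consent pages and the Data and Safety Monitoring Plan attachment are not in the supplied text and may hold a release or driving rule. Nor do the documents show that the dose is unsafe. That subjects drive is itself an inference, from the parking reimbursement in Section V.

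The end-of-night paragraph may also be carried over from another part of the project, since the same procedure names desipramine and refers to controls. It is still the only end-of-night instruction supplied.

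None of this answers the release rule itself. A late removal time or a staff member in the building does not change the stated test for leaving, which is the subject's own feeling.

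**Conclusion.** The point holds in limited form and is worth considering, with medium confidence. The release rule stated in Section V depends only on self-judged alertness, after a drug combination with listed common effects that such a test can miss, and planned contact is then about 7 days or 14 to 21 days away. It applies to 10 to 15 drug nights before repeats.

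The mismatch over signal checking is secondary. Item 6 should not suggest that signals are read after the sensors are off, but the gap is of unknown and possibly short duration.

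This rests on two assumptions: that the end-of-night paragraph applies to this study, and that no release rule exists in the consent form or safety plan. If one does, a cross-reference settles the main part, and only the wording of item 6 remains. There is no effect on the endpoints, sample size or analysis.

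**What to change.** - **Section V, end of night, both nights:** replace the self-judged exit with release by the on-site researcher or the available physician, after a brief recorded check of alertness, steadiness, heart rate and blood pressure, plus an instruction not to drive home. If the consent form or safety plan already contains such a rule, cite it instead. Keep the right to withdraw in Section IV: a subject who insists on going may go, with transport offered and the departure recorded. Using the same procedure on both nights protects the blinding.
- **Section VII, item 6:** state that heart rate, oxygen saturation and EEG are checked until study completion, with staff presence and audio/video surveillance after that for subjects who stay.

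Keeping the oximeter and EKG on until morning is optional. Section VII, item 1, notes that electrodes may disturb sleep and leave subjects tired, so it could work against the aim.

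The cost is a few sentences of text and, by assumption, a few minutes of existing staff time on each of 20 to 30 nights before repeats. Some subjects will stay longer or need other transport. Release vital signs could hint at the allocation; keeping the release form from whoever scores the recordings limits this.

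### Night order is randomised but not used in the analysis: blocking the order and adjusting for night is a cheap, minor gain in efficiency

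*Combined protocol and SAP*

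**What the plan says.** Section V (Study Procedures, Protocol) of the combined protocol and SAP states: "Two overnight sleep studies will be performed approximately 1 week apart", one on placebo and one on the combination, "in double-blinded randomized control design". Every subject receives both, so what is randomised must be the order of the nights, although the section does not put it that way.

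Section VI (Biostatistical Analysis) is the whole statistical plan. "Subjects will be prospectively enrolled until 10 had completed both study nights". That number is tied to a 50% fall in AHI with an SD of 50%. "To account for a ~30% failure rate approximately 13 patients will be enrolled in the study". Results are to be summarised as medians with interquartile ranges to limit the effect of outliers, then "data on placebo vs DAW1033D will be compared using Wilcoxon test", and "A p value < 0.05 will be considered as statistically significant".

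No section mentions period, sequence, blocking or balance between the two orders. Section IV lets a subject whose data are judged insufficient repeat all or part of the study, without saying which night the repeat stands for.

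**The concern.** The nights are heavily instrumented: a catheter in the throat, a sealed nasal mask and, where genioglossus EMG is recorded, wires placed in the tongue by needle. Section VII accepts that the electrodes may interrupt sleep and that the catheter may cause gagging. A first such night could differ from a second whatever the treatment.

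The planned test pools drug-minus-placebo differences over both orders. A night effect raises the difference in one order and lowers it by the same amount in the other. If the orders are balanced, this only adds spread, and power falls. If they are not, part of the night effect stays in the average, in a direction set by which order is more common. With 10 pairs there is little margin for either.

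**Working it through.** **Inputs.** From section VI: 10 completers, about 13 enrolled, AHI effect 50% with SD 50%, alpha 0.05. Assumptions:
- the SD is that of the paired difference;
- the test is two-sided;
- Wilcoxon means the paired signed-rank test;
- the 80% power, stated only for the EMG outcome, applies to AHI too;
- the night effect, which the documents do not give, is varied from 0 to 1 SD (0 to 50 percentage points).

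**1. The plan's own figure.** Standardised effect = 50/50 = 1. A two-sided paired t-test has power 74.8% at n = 9 and 80.3% at n = 10, so the planned 10 is reproduced. The signed-rank test at n = 10 rejects when the smaller rank sum is 8 or less (exact size 4.88%). Its power is 78.4-78.5% with normal differences and no night effect.

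**2. Model.** Subject i has drug-minus-placebo difference D = τ + sπ + e. Here s is +1 in one order and -1 in the other, π is the night effect and e has SD σ. With n1 and n2 completers in the two orders:
- The pooled mean is centred on τ + π(n1 - n2)/10. There is no bias at 5:5. The bias is 0.4π at 7:3 and 0.6π at 8:2.
- At 5:5 the spread seen by the test is about √(σ² + π²): 1.12σ at π = 0.5σ and 1.41σ at π = σ.
- Multiplying D by s gives the difference between nights, taken in one fixed direction, π + sτ + e (e with its sign changed in one order). The two orders then differ in mean by 2τ, whatever π is. The permutation test uses this contrast and all 252 relabellings at 5:5.
- The variance of that estimate of τ is σ²/(4·n1·n2/10). The effective number of pairs is therefore 10 at 5:5, 9.6 at 6:4, 8.4 at 7:3 and 6.4 at 8:2.

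**3. Power at 5:5** (simulation, normal differences, τ = σ, 100,000 trials per setting):

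| Night effect, SD (AHI points) | Signed-rank | Adjusted permutation |
|---|---|---|
| 0 | 78.5% | 77.4% |
| 0.25 (12.5) | 76.3% | 77.5% |
| 0.5 (25) | 69.9% | 77.5% |
| 0.75 (37.5) | 58.5% | 77.3% |
| 1.0 (50) | 43.9% | 77.5% |

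The two tests cross at about 0.2 SD.

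**4. Type I error of the signed-rank test, night effect 0.5 SD.** It is 2.9% at 5:5, 3.7% at 6:4, about 6% at 7:3 and 10.1% at 8:2. Averaged over simple randomisation it is 4.9%. A split of 8:2 or worse has probability 2 × (1 + 10 + 45)/1024 = 112/1024 = 10.9%.

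**5. Cost of adjusting when there is no night effect:**

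| Completers | Signed-rank | Permutation | Cost, points |
|---|---|---|---|
| 5:5 | 78.5% | 77.4% | 1.1 |
| 6:4 | 78.5% | 76.1% | 2.4 |
| 7:3 | 78.5% | 71.3% | 7.2 |
| 8:2 | 78.4% | 56.8% | 21.6 |
| Simple randomisation, average | 78.5% | 72.0% | 6.5 |
| 13 blocked as 7:6, 10 random completers | 78.5% | 76.3% | 2.2 |

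Under simple randomisation the adjusted test still trails at 0.25 SD (71.9% against 76.0%) and leads only by 0.5 SD (72.0% against 69.2%). In the 7:6 case, with the larger order the one that the night effect favours, it trails at 0.25 SD (76.3% against 77.8%) and leads at 0.5 SD (76.4% against 73.1%).

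**6. Other distributions, no night effect, signed-rank then permutation.** At 5:5: t with 5 df, 81.4% and 80.5%; t with 3 df, 85.5% and 85.4%; skewed, 73.4% and 73.1%; 10% outliers, 82.5% and 82.0% in one setting and 58.3% and 57.5% in another. At 7:3 with 10% outliers: 58.4% and 48.5%.

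**The case against.** **The planned test is sound.** A reader might infer that ignoring night order invalidates it or inflates false positives. The documents do not support that. With order randomised, type I error averages 4.9%, and at 5:5 a night effect makes the test conservative. The excess is conditional on an uneven split: slight at 7:3, and about 10% at 8:2 with an assumed 0.5 SD night effect. Blocking alone, with the planned test kept, would largely remove it. This objection stands and makes the point one of efficiency.

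**The night effect is unknown.** This also stands. A 0.5 SD effect is a 25-point shift in AHI between nights, half the targeted drug effect, and 1 SD equals the whole of it. The instrumentation makes some effect plausible but gives no size. The tongue wires are optional under section V, and AHI does not depend on them.

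**Adjustment is not always cheap.** True: the 1-point cost belongs to 5:5. Changing the test without blocking could lose more than it gains.

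**Wilcoxon was chosen to limit outliers, and the alternative uses means.** At 5:5 the cost in the heavy-tailed and outlier settings is about 1 point or less. At 7:3 with outliers it is about 8-10 points, another reason to keep the orders balanced. A rank-sum test on the night differences would keep ranks, but its exact size at 5:5 is only 3.2% and its power 67.5%, about 11 points below the signed-rank test.

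**Conclusion.** A minor, inexpensive improvement. The plan randomises order and then does not use it. At 5:5 the planned test loses about 2 points of power at a night effect of 0.25 SD, 8-9 at 0.5 SD and about 35 at 1 SD. The adjusted test holds at 77-78% throughout. Below about 0.2 SD there is no gain.

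These figures rest on a 1 SD drug effect, 10 completers, a two-sided 5% level, normal differences and an assumed night effect. They do not show that a night effect exists in this population or that the planned analysis is invalid.

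**What to change.** 1. Randomise order in blocks of 2 or 4. Let a replacement subject take the order of the subject replaced, assigned by whoever holds the list so that blinding is kept. This holds the 10 completers near 5:5.
2. Pre-specify as the main test an exact permutation test comparing the mean night-1 minus night-2 difference between the two orders. Keep the medians and interquartile ranges, and report the signed-rank test as the unadjusted sensitivity analysis.
3. State before unblinding which period a repeated night under section IV is assigned to, for full and partial repeats. The adjusted test depends on those labels.

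The change needs a blocked list and a few lines in section VI, with no extra subjects, nights or procedures. Its price, if there is no night effect, is about 1 point of power at 5:5 and 2-3 at 6:4. Because that price reaches about 7 points at 7:3 and more than 20 at 8:2, item 2 should not be adopted without item 1.
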